5.1.3 Exploratory PK Analysis set (EPKAS)

5.2 General Principles for Presenting Study Data

5.2.1 Presentation of Data

Continuous data will be summarized using descriptive statistics where the following parameters will be reported:

- Number of observations (n),
- Arithmetic Mean
- Arithmetic Standard deviation (SD),
- Median,
- · Min. and Max.
- Geometric Mean for log-normal PK parameters),
- Geometric Coefficient of Variation (CV%) for log-normal PK parameters).

Statistical Analysis Plan

CX842A2106

Version 1.0 final, 2023 Jan 16

Categorical data will be presented as the number and percentage of subjects or observations in each category.

Percentages will be based on number of subjects with data at a certain time point in the analysis set of interest except for presentations of medical history, medications, and AEs where the percentages will be based on the number of subjects in the study population.

In general, all data will be listed. All summary tables will be structured with a column for each treatment and will be annotated with the total population size relevant to that table/treatment, including any missing observations. Summary by treatment corresponds to summary by treatment ignoring period (treatment sequence), i.e., linaprazan glurate fasted (Reference formulation), x linaprazan glurate fasted (Test formulation).

TLF mock shells will be shown in a separate TLF plan.

5.2.2 Presentation of PK Data

Individual and mean PK profiles for concentrations of linaprazan glurate and linaprazan will be plotted in Phoenix® WinNonlin® and reported for all subjects in the PK analysis sets. Mean concentration data will be plotted against scheduled (nominal) sampling times while individual concentration data will be plotted against actual sampling times.

PK concentration data

All individual PK concentrations will be presented in listing tables included in the appendices of the CSR. These data will be presented and analysed with the same precision as the source data provided by the bioanalytical laboratory.

PK parameters

The derived parameters will be listed individually by subject and summarised by treatment using descriptive statistics. PK parameters and actual elapsed sample collection times will be rounded for reporting purposes in by-subject listings.

PK data will be presented by treatment using summary statistics with number of measurements, arithmetic mean, SD, as well as median, minimum and maximum values. For the PK parameters AUCinf, AUClast, and Cmax, the geometric mean and geometric coefficient of variation (CV%) will also be presented. For the PK parameters T_{max} and $T_{1/2}$, only the median, minimum, and maximum values will be presented. For the PK parameter AUC_{extrapol%}, the geometric mean and CV% will also be presented. All data will be listed by treatment and subject.

Individual and mean linaprazan glurate and linaprazan plasma concentrations will be plotted against time for each treatment (A, B and C).

In export datasets, PK parameters will be provided with full precision, and will not be rounded. Descriptive statistics of PK parameter data will be calculated using full precision values and rounded for reporting purposes only.

5.3 Statistical/Analytical issues

5.3.1 Missing Data and Handling of Dropouts

All available data will be used in the statistical analysis. A subject who withdraws prior to the last planned visit in the study will be included in the analyses up to the time of discontinuation. No imputation of missing data will be performed.

Statistical Analysis Plan

CX842A2106

Version 1.0 final, 2023 Jan 16

Concentration results that are below the lower limit of quantification (LLOQ) will be identified as below limit of quantification or not quantifiable (NQ) by the Bioanalysis lab.

For the PK analysis and plots of data, values <LLOQ before the first observed concentration will be entered as zero and values <LLOQ at any other time point will be excluded from the analysis (i.e. handled as missing data). The handling of these values will be justified and documented. Not quantifiable samples will be treated as missing data. In plots, the method used for handling values <LLOQ will be described in a footnote.

No value of AUC_{inf}, $t_{1/2}$, CL/F and V/F will be reported for cases that do not exhibit a good estimate for the terminal log-linear phase in the concentration versus time profile (for details see 5.6).

5.3.2 Outliers

In general, no outliers will be removed from analyses. However, if an outlier is identified in the PK analysis sets, an outlier analysis will be performed to determine the outlier effect on study results.

5.3.3 Data Transformations and Derived Variables

The natural-log (In) transformation will be made for the PK parameters AUC_{last} , AUC_{inf} and C_{max} prior to calculating the ratios of these parameters for the Test and Reference products and obtaining the confidence intervals for the ratios.

5.3.5 Multicentre Studies

The study will be performed at a single centre.

Statistical Analysis Plan

CX842A2106

Version 1.0 final, 2023 Jan 16

5.4 Disposition and Background Information data

Descriptive summaries for continuous data and for categorical data will be provided in accordance with Section 5.22.

5.4.1 Subject Disposition

Number of subjects screened, screening failures, randomized, randomized and not taken IMP, randomized and taken IMP, completing the study, withdrawals (including withdrawal reason) and number of subjects in each analysis set will be summarized by treatment sequence.

5.4.2 Protocol Deviations

Protocol deviations, and implications of the deviations, will be presented in listings.

5.4.3 Demographic and Baseline Characteristics

Demographic and baseline data will be summarized as appropriate depending on the data type by treatment sequence.

5.4.4 Medical History

Medical history will be coded by system organ class (SOC) and preferred term (PT) using MedDRA and presented as number and percentage of subjects in each SOC and PT by treatment sequence and will be presented in listings.

5.4.5 Prior and Concomitant Medications

Prior medications will be coded in the electronic data capture (EDC) system using WHODrug preferred terms.

5.4.6 Treatment Compliance

IMP administered will be listed by subject and sequence.

5.4.7 Premature Discontinuation

Subjects who discontinue the study prematurely will be summarized by reason for early discontinuation and treatment sequence.

5.5 Safety Analyses

No formal analyses will be performed for safety endpoints. Descriptive summaries for continuous and categorical safety data will be provided in accordance with Section 5.2 if not otherwise stated. Complete listings of all subject safety evaluations will be provided to support each summary table.

All presentations will be based on the full analysis set.

5.5.1 Adverse Events

All adverse events (AEs) occurring during this clinical trial will be coded using the Medical Dictionary for Regulatory Activities (MedDRA) version 24 or later.

AEs will be tabulated by System Organ Class (SOC) and Preferred Term (PT). Summary tables will include number of subjects reporting the AE and as percent of number of subjects dosed by treatment.

AEs will be counted as follows:

Statistical Analysis Plan

CX842A2106

Version 1.0 final, 2023 Jan 16

- In summaries of number of subjects experiencing AEs, subjects with more than one AE within a particular SOC are counted only once for that SOC. Similarly, subjects with more than one AE within a particular PT are counted only once for that PT.
- In summaries of number of subjects experiencing AEs, subjects reporting a TEAE more than once within that SOC/PT, but with different severities or different relationships, the worst category of severity/relationship will be used.
- If the severity or relationship is missing for a TEAE, it will be considered as missing in the summary tables.

All AEs will be listed in by-subject data listings including verbatim term, MedDRA coded term, treatment, severity, relationship to IMP and action taken with respect to IMP.

SAEs will be summarised and listed separately. The summary will include number of SAEs as well as the number and percentage of subjects reporting any SAE by SOC and PT for each treatment.

5.5.2 Laboratory Evaluations

Descriptive summaries for clinical chemistry, haematology, coagulation and urinalysis including absolute and relative (%) change from their baselines will be presented by treatment.

All laboratory parameters for individual subjects will be listed and subjects with clinically significant (according to the Investigator's criteria) abnormal values (out of normal range reported by the laboratory) will be flagged and listed separately. The categorization of laboratory parameter observations into 'normal' 'abnormal, not clinically significant', or 'abnormal, clinically significant' will be summarized using shift-tables (baseline category versus the worst observed categorization over time points post baseline) by treatment).

5.5.3 Concomitant Medications

Concomitant medications will be summarized using WHO Drug preferred names and show number and percentage of subjects per preferred name.

All data will be presented by treatment and summarized overall, as well as presented in listings by treatment sequence and subject.

5.5.4 Physical Examination

Physical examination will be presented as the number and percentage of subjects with normal, abnormal not clinically significant, abnormal clinically significant result over time by Body System and treatment.

5.5.5 Vital Signs

Vital signs will be summarised by treatment. The summary will include change from baseline at each visit.

5.5.6 Electrocardiogram

Summaries of ECG results and change from baseline over time will be presented by treatment.

The last measurement taken before dose intake.

5.6 Pharmacokinetic Analyses

The PK analysis will be performed based on the PK analysis set and Exploratory PK analysis set. All PK analyses will be performed according to the actual treatment and dose received. Actual sampling time points relative to dosing will be used in the calculations. Pre-dose concentration values will be excluded from the NCA and set to 0.

Statistical Analysis Plan

CX842A2106

Version 1.0 final, 2023 Jan 16

The parameters to be determined in the study are presented in section 4.7. Parameters directly derived from the plasma concentration – time plot are not further described (i.e. C_{max} , t_{max}), but all other calculations to be performed are described in detail below. Missing sample around the anticipated tmax may be flagged as "not accepted" upon decision by the pharmacokineticist.

For subjects with insufficient PK data available leading to an extrapolated AUC (%Extrap AUC) exceeding 20%, the parameters depending on λ_7 (AUC_{inf}, $t_{1/2}$, CL/F, and V/F) will not be reported.

Estimation of the terminal elimination rate constant (λ_z)

The terminal elimination rate constant (λ_z) is calculated by log-linear regression of the terminal portion of the plasma concentration time profile. At least three observations will be used to estimate λ_z and the data points used in each estimation are indicated in the individual PK profiles. Data points for calculation of $t_{1/2}$ via λ_z are selected based on visual inspection of log-concentration-time plots of individual profiles and adjusted if needed. Any exclusion of data points in the terminal phase for this estimation should be clearly justified in the PK analysis log.

The adjusted R^2 should be considered in the selection of samples for calculation of λ_z and preferably exceed a value of 0.8. If λ_z cannot be reliably estimated, resulting in a low value of R^2 , it will be flagged as "not accepted" and the associated parameters (AUC_{inf}, $t_{1/2}$, CL/F, and V/F) may be reported as "not determined".

Use of λ_z values obtained from data spanning less than three half-lives is permissible on the judgement of the pharmacokineticist provided that the resulting extrapolated area is not more than 20% of the total AUC determined. The % of extrapolated AUC will be presented for all subjects.

Area under the plasma concentration-time curves (AUCs)

The area under the plasma concentration-time curves (AUCs) are calculated using the linear up -log down method (i.e. linear trapezoidal rule is used when concentration data is increasing and the logarithmic trapezoidal rule is used when concentration data is decreasing) using uniform weighing.

AUC_{inf} is calculated based on the AUC_{last} (AUC from time of dosing to the time point of the last quantifiable plasma concentration) and then extrapolated to infinity using the concentration in the last quantifiable sample (Clast) and the estimated terminal elimination rate constant (λ_z), as follows:

AUC_{inf}= AUC_{last}+ (C_{last}/λ_z) terminal half-life ($t_{1/2}$) The half-life is calculated by ln2/ λ_z . Apparent total clearance (CL/F)

Total body clearance for extravascular administration, CL/F= Dose/AUC_{inf}

Apparent volume of distribution (V/F) Volume of distribution based on the terminal elimination phase, V/F =Dose/($\lambda z*AUC_{int}$) Relative Bioavailability (F)

The assessments of relative bioavailability will be based upon 90% confidence intervals for the ratios of the population geometric means (Treatment B [Test]/Treatment A [Reference]) for AUC_{inf} , AUC_{last} , and C_{max} , which will be obtained from the Linear Fixed Effects model described in Section 5.6.1.

The food effect evaluation will be based upon 90% confidence intervals for the ratios of the population geometric means (Treatment C [Test, fed] /treatment B [Test, fasted]) for AUC_{inf} , AUC_{last} , and C_{max} .

Statistical Analysis Plan

CX842A2106

Version 1.0 final, 2023 Jan 16

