2.2 Secondary Objectives

- To evaluate the relative bioavailability of linaprazan glurate between the test formulation of linaprazan glurate and the previously study reference formulation after the administration of single 100 mg doses in fasting conditions.
- To assess the effect of a high-fat, high-calorie meal, in comparison to fasting conditions, on the PK of linaprazan glurate after the administration of single 100 mg doses of the test formulation.
- To collect additional PK data on linaprazan glurate and linaprazan after single 100 mg doses of the test formulation.
- To assess the safety and tolerability of single oral doses of 100 mg of linaprazan glurate.

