2.4 Secondary endpoints (PK)

- Relative bioavailability of linaprazan glurate for the test formulation vs. reference formulation of linaprazan glurate, based on the means ratios for AUCinf, AUClast and Cmax.
- Relative bioavailability of linaprazan glurate under fed conditions vs. fasting conditions, based on the means ratios for AUCinf, AUClast and Cmax.
- Additional linaprazan glurate and linaprazan PK parameters after single 100 mg doses of the linaprazan glurate test formulation in fasting and fed conditions:
 - Time to Cmax (Tmax)
 - Delay between the time of dosing and the time of appearance of plasma concentration (Tlag)
 - o Terminal elimination half-life (T1/2)
 - o AUC percent extrapolation (AUCextrapol%)
 - Apparent clearance (CL/F)
 - Apparent volume of distribution (Vz/F)

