4.7 Pharmacokinetic Assessments

Blood sampling time points for PK analyses and their allowed sampling time windows are detailed in section 8.1, 11.1 and 11.3.1 of the CSP. The actual blood sampling time points will be recorded in the CRFs

Plasma samples for determination of plasma concentrations and PK characterization of linaprazan glurate and linaprazan will be analyzed

The PK

parameters to be determined are listed and defined below. For further details regarding the calculation of these parameters, see section 5.6.

PK parameters:

The following PK parameters will be obtained or calculated from the plasma concentration-time data of linaprazan glurate and linaprazan, after dosing with Treatment A (Reference formulation, fasting condition), B (Test formulation, fasting condition) and C (Test formulation, fed condition) if sufficient data is available:

- AUCinf (the area under the concentration-time curve from time zero extrapolated to infinity)
- AUClast (area under the concentration-time curve from time zero to time of last measurable observed concentration)
- Cmax (maximum observed concentration)
- \bullet T_{lag} (Delay between the time of dosing and the time of appearance of plasma concentration), if applicable
- T_{max} (time to maximum observed concentration)
- λ_z (elimination rate constant)
- T_{1/2} (terminal half-life)
- CL/F (apparent total clearance)
- V/F (apparent volume of distribution)

Additional PK parameters may be determined if deemed appropriate.

How the PK parameters are determined are further described in section 5.6

Statistical Analysis Plan

CX842A2106

Version 1.0 final, 2023 Jan 16

5. Analysis Methods

All statistical analyses will be performed using SAS® (Version 9.4 or higher, SAS Institute Inc., Cary, NC, USA).

All PK analyses will be performed on individual plasma concentration-time data by non-compartmental analysis (NCA) using the software Phoenix WinNonlin® 8.3 or higher (Certara Inc, Princeton NJ, United States). An interim evaluation of PK and safety data will be performed when all subjects finalized sampling after their first dose.

All final statistical and PK analyses will be performed after this SAP is finalized and approved, the Clean File Report including decisions on analysis sets has been signed, and the database has been locked.

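### Does the single Dose/AUCinf rule in SAP section 5.6 mis-scale CL/F and V/F of the metabolite linaprazan?

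*SAP*

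**What the plan says.** Section 2.4 lists CL/F and Vz/F among the secondary endpoints for both compounds: "Additional linaprazan glurate and linaprazan PK parameters after single 100 mg doses of the linaprazan glurate test formulation in fasting and fed conditions". Section 4.7 repeats the request under Treatments A, B and C, with parameters "obtained or calculated from the plasma concentration-time data of linaprazan glurate and linaprazan".

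Section 5.6 supplies the formulas. Apart from values read directly off the profile, it says that "all other calculations to be performed are described in detail below". For clearance it gives "Total body clearance for extravascular administration, CL/F= Dose/AUC_{inf". V/F, described as "Volume of distribution based on the terminal elimination phase", is Dose/(λz × AUCinf). Neither formula has a version for a particular analyte.

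Two other statements bear on the numerator. Section 5.6 says "All PK analyses will be performed according to the actual treatment and dose received". The dose visible in the objectives is an amount of the parent compound, as in section 2.2: "To assess the safety and tolerability of single oral doses of 100 mg of linaprazan glurate". The visible SAP gives no molecular weight, linaprazan-equivalent dose or concentration unit.

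**The concern.** Section 2 of the SAP describes linaprazan as the active metabolite of linaprazan glurate, so it is not the compound that is swallowed. Taken at face value, the rule divides a mass of one compound by the exposure to another. With concentrations in mass units, CL/F and V/F of linaprazan would then carry the molecular-weight ratio of the two compounds as a constant factor. More subjects would not reduce it.

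Linaprazan is the analyte of both primary objectives, and collecting further PK data on it is a secondary objective. Two analysts who made different choices could report different absolute values for a named secondary endpoint, in a section that claims to describe its calculations in full.

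**Working it through.** The SAP states no figure on this point, so there is none to reproduce. The check is algebraic, with illustrative numbers.

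**Inputs**
- D = 100 mg of linaprazan glurate (sections 2.1, 2.2, 2.4).
- CL/F = Dose/AUCinf and V/F = Dose/(λz × AUCinf) (section 5.6).
- M = MW(linaprazan glurate)/MW(linaprazan): not in the SAP; assumed 1.0 to 1.5.
- AUCinf of linaprazan = 5 mg·h/L: assumed, for illustration only.

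**Step 1: size of the factor, with mass concentrations.** The linaprazan-equivalent dose is D/M. Unconverted over converted CL/F is (D/AUCinf) ÷ ((D/M)/AUCinf) = M. The same holds for V/F, because λz does not use the dose. The relative error is M − 1. The unconverted CL/F is 100/5 = 20.0 L/h.

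| M (assumed) | 100/M (mg) | CL/F with converted dose (L/h) | Error if unconverted |
|---|---|---|---|
| 1.0 | 100.0 | 20.0 | 0% |
| 1.1 | 90.9 | 18.2 | +10% |
| 1.2 | 83.3 | 16.7 | +20% |
| 1.3 | 76.9 | 15.4 | +30% |
| 1.4 | 71.4 | 14.3 | +40% |
| 1.5 | 66.7 | 13.3 | +50% |

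The upward direction is itself an assumption: it needs M above 1, which the SAP does not state.

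**Step 2: molar units.** With dose and concentrations both molar, the dose is D/MW(glurate) and the AUC is AUCinf/MW(linaprazan). The quotient is (D/M)/AUCinf, the converted value, so there is no error. A mg dose over a molar AUC would not come out in volume per time, so that slip would show in the units.

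**Step 3: what depends on the dose basis.**
- AUCinf, AUClast, Cmax, λz and AUCextrapol% do not use the dose.
- Half-life is ln2/λz. Written as ln2 × (V/F)/(CL/F), M cancels.
- Ratios of CL/F between treatments at equal dose: for AUCs of 5 and 6 (ratio 6/5 = 1.2), the CL/F ratio is (100/6)/(100/5) = 0.833. Replacing 100 by 100/M in both terms leaves 0.833.
- The models in section 5.6.1 are fitted to ln AUCinf, ln AUClast and ln Cmax only, so no geometric mean ratio or 90% confidence interval changes.

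**Step 4: does the SAP prescribe the unconverted dose?** It does not. The sentence on treatment and dose received most naturally means analysis by what was actually taken rather than what was allocated. It does not say whether a metabolite's dose is expressed as parent mass or as equivalents. In the public copy the descriptions of Treatments A, B and C in section 3.1 are blank, and the bioanalysis sentence in section 4.7, "Plasma samples for determination of plasma concentrations and PK characterization of linaprazan glurate and linaprazan will be analyzed", breaks off. Dose details could stand in the first place and concentration units in the second.

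**The case for a change.** The strongest case for a change is that section 5.6 takes on the calculation of linaprazan CL/F, claims completeness, and leaves the numerator undefined. Concentration units alone would not settle what Dose means for a metabolite. That the values are only apparent is no full answer either: F covers absorption and extent of conversion, whereas a mass mismatch between two compounds is a separate and avoidable factor.

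The error could also exceed sampling error. With the 42 evaluable subjects of section 3.4.1 and an assumed between-subject CV of 20% to 60%, s = √ln(1 + CV²) runs from 0.198 to 0.555. The upper 90% limit of a geometric mean, exp(t(0.95, 41) × s/√42) − 1, then lies 5.3% to 15.5% above the estimate. An M of 1.2 or more would exceed that throughout.

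It stands that the visible text does not give the dose basis and that one clause would supply it. The comparison with sampling error carries little weight. It sets one assumed quantity against another, and sections 5.6 and 5.6.1 plan no confidence interval for CL/F or V/F. The claim of completeness is met by correct formulas; an unstated unit convention does not contradict it. The mis-scaling arises only if the analyst also chooses an unconverted mass dose, which the SAP does not ask for.

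**Conclusion.** No change to the plan follows. The formulas are right, and what is missing is a convention that a pharmacokineticist ordinarily settles when setting up the non-compartmental analysis.

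The possible effect is a constant factor M on two descriptive parameters of one analyte. It is 10% to 50% for an assumed M of 1.1 to 1.5, and nil if dose and concentrations are both molar. Neither M, nor its being above 1, nor the concentration units can be established from the SAP, so inflation is a conditional possibility and has not been shown. Because the factor is constant, a single division would correct it at reporting without new data. CL/F and V/F of linaprazan would still be apparent values afterwards, with bioavailability and extent of conversion unknown. The primary comparisons, the other PK parameters and every between-treatment ratio are the same under either dose basis.
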